5.14.2.1. Overall Summary of Adverse Events

An overall summary of AEs will be provided to summarize the following categories using frequency counts and percentages:

- patients with at least 1 TEAE, SAE, or CTCAE Grade 3 or 4 or 5 TEAE
- patients with AEs that led to death (all, up to 30 days after last dose of study drug), or discontinuation of study drug regimen
- patients with SAEs that led to discontinuation of study drug regimen

The summary will be provided for regardless of study drug causality, and repeated for events deemed by the investigator to be related to study treatment. Comparison between the treatment groups will be performed using Fisher's exact test.

5.14.2.2. Treatment-Emergent Adverse Events (TEAEs)

An overview of TEAEs will be provided to summarize the number and percentage of patients with any:

- TEAE
- treatment-emergent SAE

- CTCAE Grade ≥ 3 TEAE
- $>5\%$ by experimental arm
- TEAE leading to death (on treatment and within 30 days of last dose of study drug)
- TEAE leading to discontinuation of olaratumab, chemotherapy, or any study drug
- TEAE leading to dose modification of any study drug, olaratumab, or chemotherapy
- TEAE leading to hospitalizations
- TEAE leading to transfusions
- TEAE by cycle

The numbers and percentages will be calculated based on overall (regardless of causality), possibly related to olaratumab, chemotherapy, or any study drug for the overview of TEAEs.

In addition, the following TEAE summaries will be provided (regardless of causality, and study-drug related):

- summary of TEAEs by SOC and PT
- summary of TEAEs by high level group term (HLGT) and high level term HLT
- summary of TEAEs by worst CTCAE grade and PT
- summary of TEAEs by PT and decreasing frequency
- summary of TEAEs by AESI and consolidated category and PT

A patient listing of all AEs will be provided.

5.14.3. Deaths, SAEs, and Other Significant AEs

Deaths

The following death reports will be provided:

- summary of deaths (all deaths and deaths within 30 days of last dose of study drug) and their primary cause (study disease progression, AE, other)
- listing of treatment-emergent adverse events leading to death

SAEs

The following SAE summaries will be provided:

- summary of treatment-emergent SAE by SOC and PT
- summary of study drug-related treatment-emergent SAE by SOC and PT
- summary of AESI and consolidated treatment-emergent SAEs
- summary of study drug-related consolidated treatment-emergent SAEs

A listing of SAEs will be produced.

AE of special interest (AESIs)

The following AESI analyses will be provided:

- overview of treatment-emergent AESI (regardless of causality and study drug-related)
- summary of treatment-emergent AESI by AESI group and PT (regardless of causality and study drug-related)

- listing of treatment-emergent AEs of IRR
- listing of treatment-emergent AESIs (cardiac arrhythmia and cardiac dysfunction)

Consolidated AEs

Any AE summary table that has the need for consolidation will include a summary of the corresponding consolidated AEs in the table. The associated synonymous PTs will also be presented under each consolidated AE. Events will be ordered by decreasing frequency of PTs and consolidated AEs will be presented alphabetically. The following analyses include consolidated AEs:

- summary of TEAEs by worst CTCAE grade and PT
- summary of TEAEs by PT and decreasing frequency
- summary of TEAEs by consolidated category and PT
- summary of consolidated treatment-emergent SAEs
- summary of study drug-related consolidated treatment-emergent SAEs
- summary of TEAE on Core Safety Information criteria

Other significant adverse events

The following analysis will be provided:

- summary of TEAEs that led to discontinuation of any study drug, olaratumab, or chemotherapy by SOC and PT
- summary of TEAEs that led to dose modification of any study drug, olaratumab, or chemotherapy by SOC and PT
- listing of TEAEs leading to discontinuation of study drug
- listing of TEAEs leading to study drug dose modifications

5.14.4. Clinical Laboratory Evaluation

The severity of laboratory results will be classified according to CTCAE Version 4.0. The shifts in CTCAE toxicity grading from baseline to worst grade postbaseline (first dose up to 30 days after the last dose of study treatment) will be produced.

A patient listing of all laboratory data will be provided with a flag for values outside of the laboratory normal range as well as investigator site, patient identifier, age, gender, race, weight and visit.

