Safety: Safety analyses will be performed on the safety population (that is, all randomized patients who received at least 1 dose, including a partial dose, of any study treatment, and will include summaries of incidences of treatment-emergent adverse events (TEAEs) by maximum CTCAE grade that occurred during the study treatment period or within approximately 30 days after the decision is made to discontinue study treatment. Additionally, the following (but not limited to) safety-related outcomes will be summarized: study treatment discontinuation due to TEAEs, deaths during the study treatment period or within 30 days after the decision is made to discontinue study treatment, treatment-emergent serious adverse events (SAEs) during the study treatment period or within 30 days after the decision is made to discontinue study treatment, hospitalizations, and transfusions during the study treatment period or within 30 days after the decision is made to discontinue study treatment.

Adverse events (AEs), including TEAEs, will be listed and summarized in frequency tables using MedDRA. Severity of AEs will be graded using CTCAE version 4.0. Other safety data, such as laboratory tests, ECGs, echocardiogram (ECHO) or MUGA scans, and vital signs will be listed and summarized, if appropriate.

Patient-Reported Outcomes (PROs): For each instrument (mBPI-sf, EORTC QLQ-C30, and EQ-5D-5L), percentage compliance will be calculated as the number of completed assessments divided by the number of expected assessments (that is, patients still on study and alive). Data will be separately summarized by treatment and time point using descriptive statistics. Analyses of time to first worsening of pain as well as HRQoL domains and sub-domains will be conducted.

Immunogenicity: Incidence of anti-olaratumab antibodies will be tabulated. Correlation to olaratumab drug level, activity, and safety will be assessed, as appropriate.

Pharmacokinetics: The PK parameters of olaratumab will be computed by nonlinear mixed effect modelling using [REDACTED]. PK data collected for doxorubicin will be analyzed using descriptive methods.

Biomarkers: Analyses will be performed on biomarkers relevant to pathways associated with STS, the mechanism of action of olaratumab or doxorubicin, and/or cancer-related conditions. Assay results will be summarized and correlated with clinical outcomes.

3. Table of Contents

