- **Baseline:** begins when the ICF is signed (study entry) and ends at the first study treatment (or at discontinuation, if no treatment is given).
- **Study Period:** begins at the first study treatment and ends at study completion.
 - **Study Treatment Period:** begins at the first study treatment and ends when the patient and the investigator agree that the patient will no longer continue study treatment. The date of this agreement is to be reported on the electronic case report form (eCRF) as the Date of Discontinuation from study treatment.
 - **Post discontinuation Follow-Up:** begins the day after the patient and the investigator agree that the patient will no longer continue study treatment.
 - **Short-term follow-up** begins the day after the patient and the investigator agree that the patient will no longer continue study treatment and lasts approximately 30 days (± 7 days). The short-term follow-up visit occurs at or near the end of the short-term follow-up period (± 7 days).
 - **Long-term follow-up** begins the day after short-term follow-up is completed.
 - **Follow-up for progression** - Patients that discontinue study treatment for reasons other than progression will be assessed for progression every 6 weeks (± 7 days) until PD.
 - **Follow-up for survival** - Patients will be followed every 3 months (± 2 weeks) for the first year, every 6 months (± 2 weeks) the second year, then annually [± 2 weeks] thereafter until the patient's death or overall study completion.
- **Continued Access Period:** begins after study completion and ends at the end of trial. During the continued access period, patients on study treatment who continue to experience clinical benefit and no undue risks may continue to receive olaratumab treatment until one of the criteria for discontinuation is met. The continued access period includes continued access follow-up. Refer to Section 8.1.4 for more details.

- Continued access follow-up: begins the day after the patient and the investigator agree that the patient will no longer continue treatment in the continued access period and lasts approximately 30 days (± 7 days). The continued access follow-up visit occurs at or near the end of the continued access follow-up period.

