To maintain a concomitant administration schedule of olaratumab/placebo and doxorubicin on Day 1 of the first 8 cycles, a delay in olaratumab/placebo administration will be allowed to match the corresponding delay in doxorubicin due to toxicity. For the same reason, a delay in doxorubicin administration will be allowed to match the corresponding delay in olaratumab/placebo due to toxicity. Treatment may be delayed for up to 21 days (1 equivalent cycle) to allow a patient sufficient time for recovery from study drug-related toxicity. If a patient does not recover from the toxicity within 42 days (2 equivalent cycles) from last dose, then the patient must be discontinued from study therapy.

Dose Modifications:

Any patient who requires a dose reduction will continue to receive the reduced dose for the remainder of the study. Any patient who has had 2 dose reductions and who experiences a toxicity that would cause a third dose reduction must be discontinued from study treatment.

Since all investigators are blinded to treatment arms, they will treat all patients as if the patient received study drug versus placebo and will adjust doses accordingly.

In the event of an alteration in olaratumab/placebo dose due to an olaratumab/placebo-related toxicity, doxorubicin need not be altered, and the planned doxorubicin schedule should be maintained.

Similarly, olaratumab/placebo therapy need not be altered or discontinued for doxorubicin-related toxicity. An alteration in doxorubicin dose will always necessitate a corresponding change in dexrazoxane dose, if administered, in order to maintain a dosage ratio of 10:1 (dexrazoxane:doxorubicin).

Discontinuations:

In general, discontinuation of 1 study drug (olaratumab/placebo or doxorubicin) will not necessitate discontinuation of the other study drug. Any changes in treatments being added to or removed from patient care will be recorded on the eCRF.

In the event of discontinuation of olaratumab/placebo therapy due to an olaratumab/placebo-related toxicity, doxorubicin need not be altered, and the planned doxorubicin schedule should be maintained. In the event that olaratumab/placebo treatment is discontinued for reason of toxicity, the patient may continue treatment with doxorubicin through Cycle 8 at the discretion of the investigator.

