5.2.1.2. Safety Analysis Variables

Definitions of variables for safety analysis are listed by category and alphabetically within category.

Adverse event (AE)-related variables are listed below:

- **Adverse event (AE)** is defined as any untoward medical occurrence in a patient administered a pharmaceutical product, without regard to the possibility of a causal relationship.

AEs of special interest (AESIs)

AESI for olaratumab:

- Infusion-related reactions (IRRs)

AESI for doxorubicin:

- Cardiac arrhythmias
- Cardiac dysfunction

AESI for the combination of olaratumab and doxorubicin:

- IRRs
- Cardiac arrhythmias
- Cardiac dysfunction

Notes.

Categories of AESI may be modified as the understanding of the safety of the investigational drug increases. The final list of categories will be maintained at both compound and study level and reported in the CSR.

Consolidated AEs are composite AE terms consisting of synonymous PTs to allow meaningful interpretation of the AE data. Consolidated AE categories and PTs will be maintained at compound and/or study level and reported in the CSR.

Serious adverse event (SAE) is any AE that results in one of the following outcomes:

- death
- a life-threatening experience (that is, immediate risk of dying)
- persistent or significant disability/incapacity
- initial or prolonged in-patient hospitalization
- congenital anomaly/birth defect
- considered significant by the investigator for any other reason

Treatment-emergent adverse event (TEAE) is defined as an event that first occurred or worsened in severity after baseline and up to 30-day short-term follow-up visit.

Exposure-related variables are listed below:

- **Number of dose level reductions:** Sum of the number of dose level reductions as reported in the eCRF
- **Dose delays:** As reported in the eCRF
- **Dose withheld/skip (Not Administered):** As reported in the eCRF
- **Dose interruption(intravenous hold due to IRR):** As reported in the eCRF

Olaratumab or placebo treatment:

- Duration of treatment (weeks; 21 days added to duration of treatment because administration is every 3 weeks [on Days 1 and 8 of each 3-week cycle]) = $([\text{Date of last cycle Day 1} - \text{date of first dose}] + 21) \div 7$
- Cumulative dose, dose intensity, and relative dose intensity:
 - Cumulative dose (mg/kg) = Sum of (dose administered at each infusion [mg] \div Last available weight [kg])

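### The SAP times its 30-day death counts and lab-shift tables from last dose, while the protocol's death window and the SAP's other safety windows follow the decision to discontinue

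*SAP*

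**What the plan says.** **Windows that end 30 days after last dose (SAP)**
- 5.14.4, laboratory shifts: "worst grade postbaseline (first dose up to 30 days after the last dose of study treatment".
- 5.14.3, deaths: "summary of deaths (all deaths and deaths within 30 days of last dose of study drug".
- 5.14.2.2, overview of treatment-emergent events: "TEAE leading to death (on treatment and within 30 days of last dose of study drug".
- 5.14.2.1, adverse events leading to death: given both overall and to 30 days after last dose.

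**Windows that follow the discontinuation decision or the follow-up visit**
- Protocol synopsis, Safety: "deaths during the study treatment period or within 30 days after the decision is made to discontinue study treatment".
- SAP 5.2.1.2, treatment-emergent events: those that "first occurred or worsened in severity after baseline and up to 30-day short-term follow-up visit".
- SAP 5.14.5, hospitalizations and transfusions: through the 30-day postdiscontinuation follow-up.

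**How follow-up is timed.** Protocol 8.1 and SAP 5.2 end the study treatment period when patient and investigator agree to stop. Short-term follow-up begins the next day and lasts about 30 ±7 days. Protocol 8.1 adds: "The short-term follow-up visit occurs at or near the end of the short-term follow-up period". Protocol Attachment 1 schedules hematology, chemistry and coagulation at that visit (Visit 801).

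**The concern.** Last dose and the decision to stop are different dates, and the gap can be long. Under Protocol 9.4.1.1 a patient must come off therapy if toxicity has not resolved "within 42 days (2 equivalent cycles) from last dose", so the decision can come as late as day 42. The last-dose windows then close before the follow-up visit takes place. After a long hold they close before the treatment period itself has ended.

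At stake are the between-arm safety tables. A death shortly after discontinuation can lie inside the protocol's window and outside the SAP's 30-day count. A severe value at Visit 801, if reported as an adverse event, is treatment-emergent under SAP 5.2.1.2 and yet absent from the shift table. What is left out grows with the length of the hold, so it concerns patients who were slow to recover. Protocol 12.2.1 lets the SAP make minor changes of method if it describes and justifies them. The SAP gives no reason for the different anchor, and its revision history does not mention one.

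**Working it through.** There is no figure in the plan to reproduce; the check is calendar arithmetic.

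**Inputs**
- d = days from the last dose of study treatment to the decision to discontinue. The documents give no distribution for it. The scenarios below are assumptions taken from the dosing schedule and the delay rule: d = 7 (last dose Day 1, decision on Day 8), d = 14 (last dose Day 8, decision at the next Day 1, so 22 − 8 = 14) and d = 42 (the longest hold). d = 0, 1 and 8 show the edges.
- Visit 801 = decision + 30 ±7 days (Protocol 8.1 and Attachment 1).
- SAP window end = day 30 after last dose.
- Protocol death window end = decision + 30 days.

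**Formulas, in days after last dose**
- Visit 801 runs from d + 30 − 7 = d + 23 to d + 30 + 7 = d + 37, which is 15 possible days.
- Some part is inside the SAP lab window only if d + 23 ≤ 30, that is, d ≤ 7.
- The protocol death window ends at d + 30. The shortfall is (d + 30) − 30 = d days.
- Post-decision days that the SAP death count covers = max(0, 30 − d).

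| d | Visit 801, range (nominal) | Visit days inside lab window | Death window shorter by | Post-decision days covered |
|---|---|---|---|---|
| 0 | 23–37 (30) | 8 of 15 | 0 | 30 |
| 1 | 24–38 (31) | 7 of 15 | 1 | 29 |
| 7 | 30–44 (37) | 1 of 15 | 7 | 23 |
| 8 | 31–45 (38) | 0 of 15 | 8 | 22 |
| 14 | 37–51 (44) | 0 of 15 | 14 | 16 |
| 42 | 65–79 (72) | 0 of 15 | 42 | 0 |

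**Sensitivity to the visit window.** Protocol 8.1 attaches ±7 days to the follow-up period and again to the visit. If both apply, the earliest visit is d + 30 − 14 = d + 16. At d = 14 that is day 30, still inside. At d = 15 it is day 31, and every possible visit is outside.

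**Inside the treatment period.** At d = 42 the shortfall runs from day 31 to day 72. Days 31–42 (12 days) precede the decision and so belong to the study treatment period; days 43–72 (30 days) follow it. The footnote to the treatment schedule in Attachment 1 keeps evaluations going at least every 21 days (±3) during an interruption, so labs may be drawn in days 31–42. They fall outside the shift window. A death in those days falls outside the 30-day counts in SAP 5.14.3 and 5.14.2.1. The line in 5.14.2.2 also names on-treatment events, so whether it captures such a death depends on how on treatment is read.

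**Example.** A patient is discontinued on day 42 for non-recovery and dies on day 45. The death is 45 − 42 = 3 days after the decision, inside the protocol's window and 45 − 30 = 15 days beyond the SAP's.

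**The case against.** The strongest reply is that nothing is lost. SAP 5.14.3 also summarizes all deaths by primary cause, and 5.14.2.1 has an overall count. The day-45 death appears there and, if due to an adverse event before Visit 801, as a Grade 5 treatment-emergent event. SAP 5.14.4 lists all laboratory data, and abnormalities reported as adverse events count up to the visit. This stands, and it limits the point to the time-limited tables. It does not remove the point, because a listing does not replace a comparison by arm.

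A reader might infer that patients with toxicity are dropped from the shift table. They are not. The table takes the worst grade from first dose, so an excluded late value matters only if it is worse than every earlier one.

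A reader might infer that Visit 801 labs are always excluded in the usual patient. The documents do not support that. The 14-day gap is an assumption, imaging runs every 6 weeks irrespective of cycles, so decisions on progression need not fall on a Day 1, and the threshold for full exclusion depends on how the ±7 days is read.

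On labs, it is fair to say that there is no conflict with the protocol. Protocol 12.2.11 gives no laboratory window, and the protocol uses last-dose timing elsewhere, for concomitant medications and for adverse-event collection. The latter (Protocol 8.1.2) is a minimum for collection, not an analysis cutoff. The laboratory point is therefore one of consistency within the SAP.

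A reader might also infer bias between arms. Protocol 5.3.1 reports more neutropenia and mucositis with the combination in the phase 2 study, but not more neutropenic sepsis or febrile neutropenia, and nothing is said about holds by arm. Unequal omission is possible but unproven.

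**Conclusion.** The mismatch is real and should be corrected. For the time-limited death counts it contradicts the protocol synopsis; for the lab shifts it is an unexplained departure from the SAP's other safety windows.

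Its size is set by d. Any gap shortens the death window by the same number of days, and from d = 30 onward the SAP's 30-day death count covers no day after the decision. Scheduled Visit 801 labs are partly outside at small d and wholly outside from d = 8, or from d = 15 on the wider reading. How many patients this touches cannot be computed from the documents.

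The effect is confined to the 30-day death sub-counts, the line for treatment-emergent events leading to death, and the lab-shift tables. Efficacy is not affected. The arithmetic assumes that last dose means the last of either study drug and that the recorded discontinuation date is never earlier than that dose.

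**What to change.** **Deaths (SAP 5.14.2.1, 5.14.2.2, 5.14.3).** Replace the last-dose cutoff with the protocol's window: the study treatment period plus 30 days from the recorded date of discontinuation. Keep the all-deaths summary.

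**Lab shifts (SAP 5.14.4).** Take the worst postbaseline grade from first dose through the later of Visit 801 and 30 days after the discontinuation date; where there is no Visit 801, use the latter alone. Ending simply at Visit 801 would not do. With d = 0 and a visit on day 23, labs from days 24–30 that count now would be lost, and patients without the visit would have no end date.

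Because each new end date is at or after last dose + 30 days, 30-day death counts and worst grades can only stay the same or rise.

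**Cost.** SAP wording and reprogrammed cutoff dates; the discontinuation date is already on the eCRF. The at-risk window becomes slightly longer for patients with long holds, in whichever arm has more of them, and the table footnotes should say so.

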5.14.5. Hospitalizations and Transfusions

The frequency and percentage of patients with any hospitalizations experienced during the study treatment period or 30-day postdiscontinuation follow-up period will be summarized by treatment group. Hospitalization incidence rates will be compared between the treatment groups using Fisher's exact test. In addition, total number of days in hospital and admissions will be summarized and compared using the Wilcoxon rank sum test.

Note. Discharge date will be imputed with last contact date for hospitalizations that are still ongoing at time of analysis.

The frequency and percentage of patients with any blood transfusions received during the study treatment period or 30-day postdiscontinuation follow-up period will be summarized by treatment group. Transfusions will be further characterized by transfused blood product (for example, packed red blood cells, platelets, fresh frozen plasma, or whole blood). The proportions of patients having blood transfusions will be compared between the treatment groups using Fisher's exact test.

Details of hospitalizations and transfusions will be included in patient listings.

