8.1. Summary of Study Design

Study I5B-MC-JGDJ is a global, multicenter, randomized, double-blind, placebo-controlled, parallel-group, Phase 3 trial in patients with advanced or metastatic STS who are doxorubicin naïve but who may have had any number of prior systemic cytotoxic therapies. Previous therapy must be completed ≥ 3 weeks (21 days) prior to randomization.

Eligible patients will be randomized 1:1 into 1 of 2 treatment options (olaratumab plus doxorubicin or placebo plus doxorubicin). Randomization will be stratified by:

[figure not shown]
- Number of prior systemic therapies for advanced/metastatic disease (0 versus ≥ 1)
NOTE: Any therapy administered in the adjuvant/neoadjuvant setting will not be considered as a prior line of therapy here.
- Histological tumor type (leiomyosarcoma versus liposarcoma versus undifferentiated pleomorphic sarcoma versus other STS types)
- ECOG performance status (0 versus 1)
- Region (North America versus Europe versus Rest of World [ROW])

Patients assigned to the investigational arm will receive 2 loading doses of olaratumab at 20 mg/kg on Days 1 and 8 in Cycle 1 followed by doxorubicin 75 mg/m² IV on Day 1 of a 21-day cycle, then 15 mg/kg IV on Days 1 and 8 followed by doxorubicin 75 mg/m² IV on Day 1 of a 21-day cycle in all subsequent cycles. Patients assigned to the control arm will receive placebo (equivalent volume) IV on Days 1 and 8 followed by doxorubicin 75 mg/m² IV on Day 1 of a 21-day cycle.

Patients will receive combination treatment for 8 cycles, followed by monotherapy olaratumab or placebo until evidence of progressive disease (PD), unacceptable toxicity, death, or other withdrawal criteria are met. No crossover will be permitted.

Starting with Cycle 1, the use of dexrazoxane (in a 10:1 ratio versus doxorubicin dose) to mitigate cardiotoxicity during treatment with doxorubicin is allowed at the investigator's discretion and is recommended for all patients receiving 5 or more cycles of doxorubicin.

[Figure JGDJ.1](#) illustrates the study design.

Abbreviations: C1 = Cycle 1; C2+ = Cycle 2 and beyond; D = day;
 ECOG PS = Eastern Cooperative Oncology Group Performance Status;
 IV = intravenous, N = number of randomized patients; PD = progressive disease;
 STS = soft tissue sarcoma.

Figure JGDJ.1. Illustration of study design.

Terms used to describe the periods during the study are defined below:

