9.4. Selection and Timing of Doses

A cycle is defined as an interval of 21 days (up to 3 days delay of a cycle will be permitted due to holidays, weekends, bad weather, or other unforeseen circumstances and will not count as a protocol deviation).

Refer to Section 5.3.1 for the olaratumab dose rationale in this study.

The dose of olaratumab/placebo administered will be determined by measuring the patient's weight in kilograms on Days 1 and 8 of each cycle. The dose of doxorubicin administered will be determined by calculating the patient's body surface area (BSA) at the beginning of each cycle. If the patient's weight does not fluctuate by $\geq 10\%$ (increase or decrease) from the weight used to calculate the prior dose, the olaratumab/placebo dose will not need to be recalculated. A $\pm 5\%$ variance in the calculated total dose will be allowed for ease of dose administration.

Patients will receive combination treatment with olaratumab/placebo + doxorubicin for 8 cycles, followed by olaratumab/placebo as monotherapy until evidence of progressive disease (PD), unacceptable toxicity, death, or other withdrawal criteria are met.

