	9.1.1	Administer premedication prior to olaratumab or placebo treatment	X	X	X	X	Premedicate all patients with the following medications (or equivalent): a histamine H1 antagonist (eg, diphenhydramine) and dexamethasone intravenously 30–60 minutes prior to the olaratumab/placebo doses on Days 1 and 8 of Cycle 1. For subsequent cycles, premedicate all patients with a histamine H1 antagonist (eg, diphenhydramine) intravenously 30-60 minutes prior to each dose of olaratumab or placebo.
Study Treatment	9.2.1	Administer olaratumab or placebo	X	X	X	X	Administer until PD, unacceptable toxicity, death, or other withdrawal criteria are met. No crossover will be permitted.
	9.2.2	Administer doxorubicin	X				Administered to all patients for the first 8 cycles (unless previous unacceptable toxicity).
Patient Disposition							At the time that the patient is discontinued from any component of the study treatment or Study Participation, information regarding the patient status will be collected.

a Study procedures will be performed prior to study drug administration, except where noted (such as vital signs). In case of dose interruption, these evaluations will also be done at minimum frequency every 21 days (±3 days).

Abbreviations: BSA = body surface area; C1D1 = Cycle 1 Day 1; CT = computed tomography; CTCAE = Common Terminology Criteria for Adverse Events; D = Day; D/C = discontinuation; ECG = electrocardiogram; ECOG = Eastern Cooperative Oncology Group; eCRF = electronic case report form; IRR = infusion-related reaction; MRI = magnetic resonance imaging; PD = progressive disease; q3c = every 3 cycles; RECIST = Response Evaluation Criteria in Solid Tumors.

Study Schedule, Protocol I5B-MC-JGDJ

Perform procedures as indicated.

Post-Treatment Discontinuation Schedule

Procedure Category	Protocol Section	Procedure	Study Period	Post-discontinuation Follow-Up		Comments
			Visit	Short-Term Follow-Up	Long-Term Follow-Up	
			Duration	30 ± 7 days	802-8XX	
				See footnote for duration		
Physical Examination	10.3.1	Physical examination	X		Physical examination will include weight.	
	Att. 4	ECOG performance status	X			
	10.3.1	Vital signs	X		Includes blood pressure, pulse and temperature.	
Lab/ Diagnostic Tests	Att. 2	Hematology	X		See Attachment 2 for details.	
	Att. 2	Serum chemistry	X		See Attachment 2 for details.	
	Att. 2	Coagulation profile	X		See Attachment 2 for details.	

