Figure JGDJ.5.2. Graphical representation of testing sequence conditional on rejection of either H_{11} or H_{12} to illustrate updating of alphas at each node and weight at each edge.

Assigning $\epsilon=0.001$ initially focuses virtually all the alpha on the primary endpoints. The iterative process of subsequent updating of the graph and redistribution of α is described in [Table JGDJ.5.5](#) below and is repeated until no further hypotheses can be rejected.

Table JGDJ.5.5. Planned Alpha Spending Using Graphical Approach

Test	Node α at Analysis
1. Initial Graph (Figure JGDJ.5.1)	
LMS OS	0.005
ITT OS	0.02
2. Graph when H_{11} LMS OS is rejected (Figure JGDJ.5.2; left)	
ITT OS	0.025
2.1 PFS* (If ITT OS is further rejected)	0.025
2.1.1 ORR** (If PFS is further rejected)	0.025
3. Graph when H_{12} ITT OS is rejected (Figure JGDJ.5.2; right)	
LMS OS	0.02498
3.1 PFS* (if LMS OS is further rejected)	0.025
3.1.1 ORR** (if PFS is further rejected)	0.025
3.2. PFS* (if LMS OS is not rejected)	0.00002
3.2.1 ORR** (if PFS is further rejected)	0.00002

Abbreviations: ITT = intent-to-treat; LMS = leiomyosarcoma; ORR = objective response rate; OS = overall survival; PFS = progression-free survival.

* Information fraction for PFS events at 60% OS events interim is 82% based on design assumptions that PFS median for control arm is 4.5 months, and experimental arm is 7.15 months.

** Information fraction for ORR response at 60% OS events interim is 85% based on design assumptions that ORR in response time is 6 months for both arms, and response rate for control arm is 12% and for experimental arm is 19%.

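### The between-arm safety tests ignore time at risk, so longer treatment on olaratumab can give nominally significant excesses when the event rates are equal

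*SAP*

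**What the plan says.** SAP 5.14.5 counts hospitalizations and transfusions "during the study treatment period or 30-day postdiscontinuation follow-up period". It states that "Hospitalization incidence rates will be compared between the treatment groups using" Fisher's exact test, and it uses the same test for the proportion of patients transfused. It adds that "total number of days in hospital and admissions will be summarized and compared using the Wilcoxon rank sum test". The hospitalization rate here is a proportion of patients with any event; there is no person-time denominator.

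SAP 5.14.2.1 covers the overall AE summary: any TEAE, SAE or Grade 3 to 5 TEAE, and AEs leading to death or discontinuation. It says "Comparison between the treatment groups will be performed using" Fisher's exact test. TEAEs run to the 30-day visit (SAP 5.2.1.2).

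The length of that window follows treatment duration. Protocol 8.1 has both drugs given together through Cycle 8, "followed by monotherapy olaratumab or placebo until evidence of progressive disease (PD), unacceptable toxicity, death, or other withdrawal criteria are met". Doxorubicin stops after 8 cycles in both arms (Protocol Attachment 1). The footnote to Table JGDJ.5.5 in SAP 5.11.1 assumes that "PFS median for control arm is 4.5 months, and experimental arm is 7.15 months".

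Tests are two-sided at 0.05 (SAP 5.2), with no multiplicity control outside OS, PFS and ORR (SAP 5.6).

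**The concern.** If olaratumab delays progression, its patients stay on treatment longer and are watched for longer. More of them will then have at least one hospitalization, transfusion or AE, and they will accumulate more admissions, even when the risk per month is the same in both arms. The planned tests cannot separate that from toxicity. The distortion is largest when the drug works, which is when the safety tables matter most for benefit-risk.

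**Working it through.** **Inputs from the documents.** 230 patients per arm (322 events / 0.70 = 460 in total, SAP 5.1); PFS medians 4.5 and 7.15 months; a 30-day tail (30/30.4375 = 0.986 months); doxorubicin limited to 8 × 21 = 168 days (5.52 months). The SAP gives no power or expected event rate for the safety comparisons, so there is no planned safety figure to reproduce.

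**Assumptions.** Time to progression is exponential. Event hazards are 0.02 to 0.20 per patient-month, identical in both arms and independent of time on treatment.

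**Length of the counted window**
- Ratio of PFS medians: 7.15/4.5 = 1.59.
- With the 30-day tail, on medians: 8.136/5.486 = 1.48.
- On means (median/ln 2 = 6.49 and 10.32 months): 11.30/7.48 = 1.51.
- With equal toxicity stopping of 0.03 to 0.10 per month added (assumed), mean treatment time differs by a factor of 1.45 to 1.29.
- Mean doxorubicin time, m(1 − exp(−5.52/m)): 3.72 and 4.27 months, a ratio of 1.15.

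**Patients with any event, constant hazard λ, mean treatment time m.** P = 1 − exp(−0.986λ)/(1 + λm). At λ = 0.05:
- control: 1 − 0.952/1.325 = 28%
- olaratumab: 1 − 0.952/1.516 = 37%

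**Rejection at nominal 5% with equal hazards** (3,000 simulated trials per row)

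| Setting | Hazard per month | Any event, control vs olaratumab | Fisher | Wilcoxon, admissions |
|---|---|---|---|---|
| Constant hazard | 0.02 | 13% vs 19% | 34% | 39% |
| | 0.05 | 28% vs 37% | 51% | 62% |
| | 0.10 | 45% vs 55% | 55% | 80% |
| | 0.20 | 64% vs 73% | 51% | 91% |
| Monotherapy hazard one third | 0.02 to 0.20 | 11% vs 13% to 61% vs 69% | 12% to 37% | 14% to 67% |
| Non-PD stopping 0.05/month | 0.05; 0.10 | 24% vs 29%; 39% vs 46% | 22%; 31% | 28%; 45% |
| Non-PD stopping 0.10/month | 0.05; 0.10 | 21% vs 24%; 35% vs 40% | 13%; 17% | 16%; 25% |
| Events only on doxorubicin + 30 days | 0.02 to 0.20 | 9% vs 10% to 58% vs 62% | 5% to 16% | 7% to 21% |

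In the constant-hazard rows every rejection pointed against olaratumab. Repeat calculations widen the Fisher ranges slightly: about 30% to 58% for a constant hazard, 8% to 31% with non-PD stopping, and 4% to 16% for doxorubicin-only events. For near-universal events (95% of controls) Fisher falls to about 15%. Hospital days were not simulated; they are counted over the same window.

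**Alternatives under the same equal hazards**
- Log-rank test of time to first event, censored at the end of the window: 4.3% to 5.3% in every setting tried with constant, one-third and zero monotherapy hazard.
- One overall person-time rate of admissions: 4.4% to 5.4% if the hazard is constant, but 11% to 47% with monotherapy risk at one third and 18% to 85% if events arise only on doxorubicin.
- An overall first-event rate ratio with doxorubicin-only events: 17%, 28% and 37% at hazards of 0.02, 0.05 and 0.10, nearly all falsely favouring olaratumab.
- A rate restricted to the common window of Cycles 1 to 8 plus 30 days: 3% to 6%.

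**The case against.** **Front-loaded toxicity.** The documents suggest that much of the risk comes early. Doxorubicin ends at Cycle 8. Protocol 9.1.1 places severe infusion reactions mainly in the first cycle. Protocol 5.3 describes the phase 2 safety profile as consistent with doxorubicin. Patients also stop for toxicity or withdrawal. This stands: the constant-hazard rows are an upper case, and with doxorubicin-only events the inflation is small.

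**Existing tables.** SAP 5.14.1 summarizes exposure, SAP 5.14.2.2 lists TEAEs by cycle, and SAP 5.2 allows further exploratory analyses. These help a reader notice an imbalance. But the by-cycle table has no stated between-arm test and does not cover all hospitalizations, admissions or transfusions, and the exposure summary is not linked to events.

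**Burden.** The proportion hospitalized over the assigned regimen is a legitimate description of what patients experience. That is a reason to keep it in the tables.

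**Stronger readings that the documents do not support.** A reader might infer that the design expects treatment duration to differ by about 60%. The 1.59 is a ratio of PFS medians from an information-fraction footnote, and the SAP states no assumption about treatment duration. A reader might also infer that AEs in general are tested as counts. Fisher compares proportions of patients, only admissions and hospital days are totals, and of the AE tables only the overall summary has a stated test. Finally, no rule in the SAP turns a small p-value into a declaration of harm; the risk is that an unadjusted p-value is read that way.

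**Conclusion.** The defect is real and worth correcting. The planned Fisher and Wilcoxon comparisons mix event risk with length of observation. Under the SAP's own PFS assumption the counted window would be about 50% longer on olaratumab, less with toxicity stopping.

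How far the tests depart from 5% depends mainly on how much risk persists in monotherapy: severe if it stays constant, moderate if it falls to a third, and slight if it ends with doxorubicin. All of this rests on assumed event rates and exponential treatment times. It also requires the PFS gain to occur; with equal PFS the windows would be similar. The primary OS analysis is not affected.

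**What to change.** In SAP 5.14.2.1 and 5.14.5:

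- Keep the crude percentages and totals as a description of burden.
- Base the between-arm inference on time to first event: first AE in each summary category, first hospitalization and first transfusion, from first dose, censored at the end of the 30-day window. Use a log-rank test and a Cox hazard ratio with 95% CI.
- Compare admissions and hospital days by mean cumulative count. Alternatively, use rates with a log-time offset, reported separately for the combination period (Cycles 1 to 8 plus 30 days) and the monotherapy period.
- Do not make one overall person-time rate the main test. If risk falls after doxorubicin, longer monotherapy dilutes the olaratumab rate and can hide harm.

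The cost is SAP wording and one extra set of tables from data already collected; design, dosing and sample size do not change. Time to first event ignores repeat events, which is why the admissions and hospital-day analyses are kept alongside it.
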